## Document History

Version	Date	Changes
1.0	08MAY2024	Addressed sponsor comments and finalized
Draft 2.0	03JUL2024	
Removed interim analysis section as per sponsor request.
 
Updated section 8.4 to indicate the details of BPI-SF score analysis.
 
Updated section 13 header title to reflect the protocol and cover for both total antibodies and neutralizing antibodies analyses planned for the study.
 
Removed adverse events leading to study discontinuation section as required information is not collected in the eCRF.
 
Added new section for non-serious adverse events as required as part of EU CTR clinical trial results summary.
 
Added extra description to relevant sections detailing EU CTR requirements of clinical trial results and lay person summary as part of the EU CTR reporting managed by the sponsor.

2.0	08AUG2024	
Updated with sponsor comments on SF36 scoring and pain scores.
 
SF-36 scoring now refers to the QualityMetric User's Manual for SF-36v2 Health Survey Third Edition.
 
Addressed sponsor comment on section 5.2 and updated terminology used for protocol deviations significance categorization.

3.0	23JAN2025	
Updated List of Abbreviations.
 
Added handling of BLQ, LOD, LOQ and ULOQ values to Section 4.

		
Updated section 7 to summarize medications/therapies by the closest ATC class level if ATC class level 4 is not available.
 
Added mention of chitotriosidase activity levels plot to Section 8.4.
 
Simplified the plots details described in sections 8.3, 9.6.1 and 9.6.2.
 
Updated Section 9.2.2 to replace CO2 by bicarbonate.

4.0	16JUN2025	
Femoral neck replaced with Hips in Screening bone mineral density T-score and Z -score in Section 6.1.
 
“Z-score & T-score at lumbar spine (L1-L4); hip (femoral neck)” changed to “Z-score & T-score at lumbar spine; hip (left and right)” in Table 2-3.
 
“Z-score and T-score at lumbar spine (L1-4) and hip (femoral neck)” changed to “Z-score and T-score at lumbar spine and hip (left and right)” in Section 8.4.

## List of Abbreviations

AAVS3	Adeno-associated viral vector serotype S3
AE	Adverse Event
AESI	Adverse Events of Special Interest
ALT	Alanine aminotransferase
APTT	Activated partial thromboplastin time
AR	Adverse reaction
AST	Aspartate aminotransferase
ATC	Anatomical Therapeutic Chemical
AUC	Area under curve
BLQ	Below the Limit of Quantification
BPI-SF	Brief Pain Inventory- Short Form
bsALP	Bone specific Alkaline Phosphatase
CHIT1	Gene encoding for Chitotriosidase
CMV	Cytomegalovirus
DEXA	Dual energy x-ray absorptiometry
DLT	Dose-limiting toxicity
DMC	Data monitoring committee
ECG	Electrocardiogram
eCRF	Electronic case report form
EOS	End of study
ERT	Enzyme replacement therapy
EU CTR	European Union Clinical Trial Regulation
FACIT-Fatigue	Functional assessment of chronic illness therapy fatigue scale
GBA1	Gene encoding for $\beta$ -glucocerebrosidase
GCase	Glucocerebrosidase
GD-DS3	Gaucher Disease severity score
HRQoL	Health-related quality of life
ICF	Informed Consent Form
ICH	International Conference on Harmonisation
INR	International normalized ratio
IV	Intravenous(ly)
LFT	Liver function test
LOD	Limit of Detection
LOQ	Limit of Quantification
Lyso-Gb1	Glucosylsphingosine
MCS	Mental Component Summary Score
MedDRA	Medical Dictionary for Regulatory Activities
MRI	Magnetic resonance imaging
MTD	Maximum Tolerated Dose
NCI	National Cancer Institute
NIMP	Non-investigational medicinal product
PCR	Polymerase chain reaction
PCS	Physical Component Summary Score
PD	Pharmacodynamic
PK	Pharmacokinetic
SAE	Serious Adverse Event
SAP	Statistical analysis plan
SAR	Serious adverse reaction
SF-36	Short Form Health Survey
SOC	System organ class
SRT	Substrate Reduction Therapy
SUSAR	Suspected, unexpected, serious adverse reaction
TEAE	Treatment emergent adverse event
ULOQ	Upper Limit of Quantification
vg	Vector genomes

WHO

World Health Organization

## 1. Introduction

FLT201 is an investigational AAV-gene therapy administered as a single dose, slow intravenous (IV) infusion, that is being developed as a treatment to improve the clinical phenotype in patients with Gaucher disease type 1.

The aim of this first-in-human, Phase 1/2, open-label study is to evaluate the safety, tolerability, efficacy, and pharmacokinetics of FLT201, and to investigate the relationship of FLT201 dose to augmentation of residual glucocerebrosidase (GCase) expression (activity and concentration), and its potential to improve the clinical phenotype by reduction of cellular accumulation of GCase substrate.

The purpose of this statistical analysis plan (SAP) is to define the planned statistical methods consistent with the study objectives. This plan should be read in conjunction with the study protocols (Global (ex-US/ex-Brazil), US only and Brazil only) and is prepared in compliance with International Conference on Harmonisation (ICH). All analyses will be conducted using SAS® Version 9.4 or higher (SAS Institute Inc., Cary, North Carolina).

## 2. Objectives and Endpoints

Table 2-1 presents the primary objectives and endpoints.

**Table 2-1 Primary Objective and Endpoints - Safety**

Primary Objective	Primary Endpoints
To assess the safety and tolerability of a single IV administration of FLT201 in adults with Gaucher disease type 1 (previously treated and previously untreated).	
Primary safety variable: incidence of TEAEs (including DLTs) from Day 1 to the last follow-up visit.
 
Other safety endpoints: incidence of AEs, SAEs, and changes from baseline in vital signs, 12-lead ECG, physical examination, and laboratory assessments from Day 1 to the last follow-up visit.

Abbreviations: AE=adverse event; DLT=dose-limiting toxicity; ECG=electrocardiogram; IV=intravenous; SAE=serious adverse event; TEAE=treatment emergent adverse event.
	

Table 2-2 presents the secondary objectives and endpoints.

**Table 2-2 Secondary Objectives and Endpoints**

Secondary Objectives	Secondary Endpoints
PK: To investigate the relationship of FLT201 dose to endogenous production of GCCase.	Change from baseline to each assessment point in plasma and leukocyte GCCase activity level.
Efficacy: To assess the impact of FLT201 on: 
 
• clearance of lyso-Gb1
 
• spleen size
 
• liver size
 
• hemoglobin
 
• platelet count
 
	Change from baseline to each assessment point in: 
 
• lyso-Gb1 in plasma
 
• spleen volume measured by MRI
 
• liver volume measured by MRI
 
• hemoglobin
 
• platelet count
 

Immunologic: To describe the immune response to GCCase transgene product.	Change from baseline to each assessment point in total anti-GCCase antibody titer and neutralizing antibody titer.
Shedding: To assess viral shedding after systemic administration of FLT201.	Clearance of vector genomes (vg) in plasma, urine, saliva, stool, and semen measured by PCR test.
Abbreviations: GCCase=glucocerebrosidase; lyso-Gb1=glucosylsphingosine; MRI=magnetic resonance imaging; PK=pharmacokinetic; PCR=polymerase chain reaction, vg=vector genomes.	

Table 2-3 presents the exploratory objectives and endpoints.

**Table 2-3 Exploratory Objectives and Endpoints**

Exploratory Objectives	Exploratory Endpoints
Other efficacy/biomarkers: To assess the impact of FLT201 on: 
 
Gaucher disease severity and progression
 
bone disease
 
fatigue
 
pain
 
biomarkers
 
lung disease
 
	Change from baseline to each assessment point in: 
 
Gaucher disease severity measured by the Gaucher disease severity score (GD-DS3)
 
bone marrow burden score measured by MRI
 
bone mineral density measured by dual energy x-ray absorptiometry (DEXA) 
 
Z-score & T-score at lumbar spine; hip (left and right)
 
 
 
fatigue measured by FACIT-Fatigue
 
pain measured by Brief Pain Inventory- Short Form (BPI-SF)
 
disease activity biomarkers: chitotriosidase, CCL18
 
bone biomarkers: bsALP, osteocalcin
 
chest x-ray and pulmonary function tests
 

Pharmacokinetic: To characterize the pharmacokinetics of FLT201.	
 
AUC, peak, and steady state GCase activity levels in plasma and leukocytes (baseline to Week 38)
 
Change from baseline to each assessment point in GCase concentration (antigen levels)
 
Dose response relationship
 

Immunologic: To describe the immune response to AAVS3 capsid proteins.	
 
Immune response to AAVS3 capsid (AAVS3 antibody titer and T-cell response)
 
Change from baseline to each assessment point in immune response biomarkers
 

HRQoL: To assess the impact of FLT201 on health-related quality of life (HRQoL).	Change from baseline to each assessment point in HRQoL measured by SF-36.
Abbreviations: AAVS3=adeno-associated viral vector serotype S3; AUC=area under curve; BPI-SF=Brief Pain Inventory – Short Form; bsALP=bone-specific alkaline phosphatase; DEXA=dual energy x-ray absorptiometry; FACIT-Fatigue=Functional Assessment of Chronic Illness Therapy - Fatigue scale; GCase=glucocerebrosidase; HRQoL=health-related quality of life; MRI=magnetic resonance imaging.	

### 3. Investigational Plan

#### 3.1. Overall Study Design and Plan

FLT201-01 is a first-in-human, Phase 1/2, open label, safety, tolerability, and efficacy study in adult patients with Gaucher disease type 1. The study has two parts. Part 1 is a dose escalation scheme in previously treated patients. When the last participant in Part 1 has completed at least 12 weeks' follow-up post-FLT201 administration, a dose will be selected for Part 2 based on safety/tolerability (including DLT), PK, PD, and clinical data from participants in Part 1. Part 2 will not occur in the US.

#### Part 1: Dose Escalation in Previously Treated Patients

Up to approximately 12 participants will be enrolled across approximately 4 dose cohorts in a dose escalation scheme in previously treated patients only.

Dose escalation will be overseen by an independent data monitoring committee (DMC). The planned dose escalation scheme is explained in the protocol.

## **Part 2 (excluding US participants): Dosing in Previously Untreated Patients**

Approximately 6 participants will be enrolled across up to 2 dose cohorts.

On completion of the study, all participants will be followed under a separate long-term follow-up protocol for at least 5 years after dosing with FLT201.

The Schedule of Assessments is described in the protocol.

### **3.2. Treatments**

FLT201 drug product is supplied as a sterile Solution for Infusion in 10 mL Crystal Zenith® vials, each vial containing 5 mL extractable volume. The vials are sealed with rubber stoppers and aluminium seals with plastic flip tops.

The appropriate number of vials required for dosing is determined based on the weight of each participant and the allocated dose level (Day -1 weight should be used to determine the final dose).

On Day 1, FLT201 will be administered as a single-dose, slow IV infusion into a peripheral vein.

### **3.3. Dose Adjustment/Modifications**

#### **3.3.1. Dose Escalation**

Dose escalation will be performed by dose cohort, and the details including the provisional dose levels can be found in the protocol.

Since individual participants will only receive a single infusion of FLT201 in this study, dose modifications are not applicable. Participants may have their infusion interrupted or stopped for safety reasons based on the discretion of the investigator. All dose interruptions or discontinuations must be recorded in the participant's eCRF.

#### **3.3.2. Temporary Halt**

Further enrolment into the study will be put on hold in the event of any of the defined temporary halt rules described in the protocol.

Following a safety review by the independent DMC, the Sponsor deems it appropriate to restart the study; this can only be done following approval by all relevant competent authorities, IECs/IRBs and any local approvals required.

## **4. General Statistical Considerations**

All study data collected will be presented in data listings, and all relevant data will be tabulated and summarized by study part, dose cohort, and overall, unless stated otherwise.

Continuous data will be described using descriptive statistics (i.e., n, mean, standard deviation, median, minimum, and maximum). Categorical data will be described using the count and percentage in each category. For the summary statistics of all numerical variables unless otherwise specified, minimum and maximum will be displayed to the same level of precision as reported. Mean and median will be displayed to one level of precision greater than the data collected. Standard deviation, standard error, and confidence intervals will be displayed to two levels of precision greater than the data collected.

Missing data will not be imputed. All analyses will be based on observed cases for the safety population unless specified otherwise.

Clinical laboratory and PK results that are below the lower limit of quantification (BLQ/LOQ), below the limit of detection (LOD), above the upper limit of quantification (ULOQ) or missing will be displayed as such in the data listings.

To calculate descriptive statistics and PK parameters, all BLQ, LOQ and LOD results will be treated as half of the BLQ/LOQ/LOD values whereas all ULOQ values will be treated as the ULOQ values as applicable.

The end of the study will be defined as the last visit by the last participant. All participants will be followed up for at least 5 years in a separate long-term follow-up study.

Unless specified otherwise, baseline will be defined as the last non-missing measurement prior to the infusion of IMP.

Change from baseline is defined as: post-baseline value – baseline value.

Study Day 1 is the calendar day of the IMP infusion. Subsequent study days are calculated as the date of assessment/event – date of infusion + 1. Pre-infusion study days are calculated as date of assessment/event – date of infusion. There is no Study Day 0.

All data are summarized based on the visit name collected on the eCRF page.

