NHP plasma data supports that a dose of FLT201 at 2×10^{12} vg/kg results in plasma GCase activity in the range of 336–1308 nmol/h/mL at Day 170 post-dose (Investigator Brochure, Section 4.4.6.2).

An investigational study in Rhesus macaques (n=7) received a dose of 2×10^{12} vg/kg FLT201 (Figure 2). Plasma GCase levels increased rapidly by Day 8; some fluctuations were noted between Days 21 and 43 and levels plateaued from Day 43. The GCase plasma levels at Day 170 post-dose in this study ranged between 336 to 1308 nmol/h/mL which were consistent with GCase levels that resulted in significant and consistent substrate clearance in the *GBA*-deficient mouse study in the liver, spleen, bone marrow, and lungs. AAV2/S3 products scale well from NHP to human based on other Freeline projects and assuming linear scaling from NHP to human and taking into account the variability observed in the NHP, a dose of 4.5×10^{11} vg/kg could result in approximately 76 to 295 nmol/h/mL plasma GCase in patients. The 2×10^{12} vg/kg FLT201 dose was well tolerated in NHP with no treatment-related findings noted at the interim analysis at 6 months post-dose and is 4.4-fold greater than the proposed starting dose of FLT201 in the Phase 1/2 study.

[figure not shown]

Figure 2: Plasma GCase Activity Levels Post Single IV Infusion of FLT201 at 2×10^{12} vg/kg in Rhesus Macaques

3. Murine GLP Toxicology Data

The murine GLP toxicity study identified a NOAEL of 2.57×10^{13} vg/kg (highest dose tested) using the genome of FLT201 pseudotyped into the AAV2/8 capsid in C57bl/6 mice and is 57-fold greater than the proposed starting dose of FLT201 in the Phase 1/2 study. AAV2/8 was selected as this capsid possesses a superior ability to transduce murine hepatocytes [Nakai 2005; Gao 2002] compared to AAV2/S3 and was utilized to ensure efficient transduction to assess the impact of high vector genome levels and production of high levels of the transgene.

GCase protein. The GCase levels achieved at the NOAEL were far in excess of that expected for FLT201 in humans (>3000-fold the 250 nmol/h/mL discussed in Method 1), which would not be possible with the AAV2/S3 capsid in mice.

Using a 10x margin of safety for the NOAEL, a dose 2.57×10^{12} vg/kg using the genome of FLT201 pseudotyped into the AAV2/S3 capsid is supported by the study.

This dose does not exceed the NOAEL 2.44×10^{13} vg/kg established for the AAV2/S3 capsid safety in NHP for FLT180a in Method 4.

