13.3 Dose Escalation

13.3.1 Dose Cohorts and Dose Interval Between Participants

The planned dose escalation scheme is as follows (if subject weight is >90 kg, the dose will be calculated based on 90 kg weight):

- Cohort 1: 4.5×10^{11} vg/kg of body weight.
- Cohort 2: 1.3×10^{12} vg/kg.
- Cohort 3: 3.9×10^{12} vg/kg.
- Cohort 4: 1.1×10^{13} vg/kg.

The dose level to be tested in each cohort after Cohort 1 may be an intermediate dose between the current dose and that of the next planned dose cohort based on emerging data but would not be greater than the next planned dose. In addition, based on emerging data, including safety/tolerability, PK, PD, and clinical data, all dose cohorts may not be tested, an additional dose cohort may be added and/or a dose cohort may be further expanded beyond 3 participants. If an additional dose cohort is added the dose will not exceed 1.5×10^{13} vg/kg, which is below the NOAEL (2.57×10^{13} vg/kg).

The dose to be given is made in line with the escalation/decision rules defined in Sections 13.3.1.1, 13.3.1.2, 13.3.1.3. In all cases, safety will be assessed first followed by evaluation of efficacy.

A minimum of 4 weeks of safety/tolerability (including DLT), PK, PD, and clinical data will be assessed before dosing each participant (both within a dose cohort and before escalating to the next dose level).

All cohorts will contain at least two participants (except as described in Section 13.3.1.2). Depending on assessment of safety/tolerability (including DLT), PK, PD, and clinical data, additional participants may be treated.

Dose escalation decisions will be overseen by a DMC and will be made in accordance with the following specific rules:

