### **10.1. Data Handling**

Data rounding specifications for PK data are documented in the PK tables, listings, and figures shells.

Plasma, leukocyte, and dried blood spot (DBS) glucocerebrosidase (GCase) activity levels that are BLQ or missing will be displayed as such in the data listings.

For the calculating of descriptive statistics and PK parameters, all BLQ values will be treated as half of the lower limit of quantification.

GCase activity levels will be baseline adjusted. Baseline is defined as any collection before the administration of the IMP. An average of the screening and pre-dose collection results will be taken to determine baseline for each of the matrices. Baseline adjustment leading to results <0 will be reported as 0.

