### **10.3. Plasma, Leukocyte and DBS Pharmacokinetic Parameters**

Plasma, leukocyte, and DBS GCase baseline adjusted activity level-time data will be analyzed by non-compartmental analysis using Phoenix® WinNonlin® Version 8.3 or higher (Certara USA, Inc., Princeton, NJ). The following PK parameters will be calculated for baseline adjusted GCase activity levels, where data permit:

$C_{\max}$	Maximum observed concentration.
$T_{\max}$	Time of maximum observed concentration.
$AUC_{\text{last}}$	AUC from time 0 to the last measurable observed concentration ( $C_{\text{last}}$ ), calculated using the linear trapezoidal rule.

Actual sampling times will be used for the estimation of all PK parameters, and all available GCaSe activity level data will be included in the analysis (including resulting from samples collected outside predefined collection windows).

Plasma, leukocyte, and DBS PK parameters will be presented in data listings and summarized separately using descriptive statistics (number of observations, arithmetic mean, SD, CV, geometric mean, geometric CV, median, minimum, and maximum) by study part and cohort.  $T_{\max}$  will be summarized using number of observations, median, minimum, and maximum only.

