#### 10.4. Pharmacokinetic Statistical Analyses – Dose Proportionality (Power Model)

A non-linear Power Model will be used to assess dose-proportionality for baseline adjusted GCaSe Activity Levels in Part 1 of the study in all matrices (plasma, leukocytes, DBS). Actual dose received by each patient will be used. The proportional relationship between the expected value of each parameter  $E(y)$  and dose is written as a power function:

$$E(y) = \alpha * \text{dose}^{\beta} \text{ [Equation 1]}$$

where ' $\alpha$ ' is a constant, ' $\beta$ ' is the proportionality constant and ' $y$ ' is the parameter of interest. The exponent,  $\beta$ , will be estimated by performing a linear regression of  $\ln(\text{parameter})$  [ $C_{\max}$  and  $AUC_{\text{last}}$ ] versus  $\ln(\text{dose})$ . The exponent,  $\beta$ , is the estimated slope of the resulting regression line, since taking logs of Equation 1 gives the linear relationship:

$$\ln(y) = \alpha + \beta * \ln(\text{dose}) \text{ [Equation 2]}$$

The relationship is dose proportional when  $\beta = 1$ .

Linear regression plots of systemic exposure ( $C_{\max}$  and  $AUC_{\text{last}}$ ) versus dose will be presented using log-log scales with the power model overlaid.

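### If GCase results above the upper limit of quantification are left unresolved, the SAP's rule of setting them equal to that limit would understate Cmax, AUClast and possibly the dose-response exponent

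*SAP*

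**What the plan says.** SAP Section 4 sets one rule for clinical laboratory and PK results outside the assay range. In listings, a result "above the upper limit of quantification (ULOQ) or missing will be displayed as such in the data listings". In calculations the flag disappears. At the low end, "To calculate descriptive statistics and PK parameters, all BLQ, LOQ and LOD results will be treated as half" of the limit; at the high end, "whereas all ULOQ values will be treated as the ULOQ values as applicable".

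SAP Section 10.1, which covers GCase activity specifically, restates only the low-end rule: "For the calculating of descriptive statistics and PK parameters, all BLQ values will be treated as half of the lower limit of quantification". It is silent on results above range, so Section 4 governs.

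SAP Section 10.3 then derives Cmax, Tmax and AUClast (linear trapezoidal): "The following PK parameters will be calculated for baseline adjusted GCase activity levels, where data permit". In SAP Section 10.4 the power-model exponent "will be estimated by performing a linear regression of" the log parameter (Cmax or AUClast) on log dose, and an exponent of 1 is read as dose proportionality. No censoring term, flag or sensitivity analysis is described.

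Neither document states a ULOQ for plasma, leukocyte or dried-blood-spot GCase, or says whether samples above range are diluted and re-assayed. Protocol Section 12.5.2 leaves sample collection and processing to the laboratory manual.

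**The concern.** A result above ULOQ is right-censored: the true value is known only to be larger than the limit. Substituting the limit and treating it as exact can only lower a participant's Cmax and AUClast. Any participant with one such sample would have the limit, less baseline, reported as an observed maximum.

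The bias need not fall evenly. If expression rises with dose, a ceiling is reached first in the top cohort, which flattens the upper end of the log-log regression. The fitted exponent would then fall below its true value, which is the pattern expected from less-than-proportional expression. Capping also compresses the spread in the affected cohorts, so the biased slope would appear more precise than it is.

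The first secondary objective is the relation of FLT201 dose to GCase production. Its endpoint, change from baseline in GCase activity, is summarised under the same substitution rule. Cmax, AUClast and the dose-response model are exploratory.

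**Working it through.** **1. Reproduce the protocol's own figure.** Protocol Section 6.5.2 reports macaque plasma GCase of 336 to 1308 nmol/h/mL at 2×10^12 vg/kg and, by linear scaling, says that 4.5×10^11 vg/kg "could result in approximately 76 to 295 nmol/h/mL plasma GCase in patients".

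- 336 × (4.5×10^11 / 2×10^12) = 75.6
- 1308 × (4.5×10^11 / 2×10^12) = 294.3

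This agrees with the stated figures to within rounding.

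**2. Extend the same scaling to the planned doses** (Protocol Section 13.3.1). The central value is the geometric mean, √(336 × 1308) × dose / 2×10^12.

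| Cohort | Dose (vg/kg) | Range (nmol/h/mL) | Central value |
|---|---|---|---|
| 1 | 4.5×10^11 | 76–294 | 149 |
| 2 | 1.3×10^12 | 218–850 | 431 |
| 3 | 3.9×10^12 | 655–2,551 | 1,293 |
| 4 | 1.1×10^13 | 1,848–7,194 | 3,646 |

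The doses span 24.4-fold, and the lowest to highest predicted value about 95-fold (7,194 / 75.6). A ceiling would reach Cohort 4 first.

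**3. Simulate the Section 10.4 slope with capping.** Each simulated value y is replaced by min(y, ULOQ), and ln(y) is regressed on ln(dose) by ordinary least squares.

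Assumptions:
- True slope 1, with 3 participants per cohort.
- Log-SD 0.5. The macaque range supports this: ln(1308/336) / 2.70 = 0.50, where 2.70 is the expected range, in SDs, of seven normal values.
- ULOQ is varied because none is given.
- One value per participant, so the results describe Cmax. AUClast was not modelled.
- The baseline adjustment is ignored as small.

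| Assumed ULOQ (nmol/h/mL) | Cohort 4 values capped | Cohort 4 geometric mean / true | Mean slope, Cohorts 1–4 | Mean slope, Cohorts 1–3 only |
|---|---|---|---|---|
| None | 0% | 1.00 | 1.00 | 1.00 |
| 8000 | 6% | 0.99 | 1.00 | 1.00 |
| 3,650 (Cohort 4 median) | 50% | 0.82 | 0.94 | 1.00 |
| 2,170 (log-midpoint of Cohorts 3 and 4) | 85% | 0.57 | 0.84 | 0.98 |
| 1,290 (Cohort 3 median) | 98% | 0.35 | 0.69 | 0.91 |

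Without a cap, the sampling SD of the slope is 0.12 with four cohorts and 0.19 with three. With four cohorts it falls to about 0.09 at the two lowest limits, which is the false precision noted above.

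**4. Sensitivity to the true slope.** If the true slope is 0.8, the mean fitted slope is 0.80 at a ULOQ of 4000, 0.75 at 2000 and 0.60 at 1000.

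**The case against.** The strongest reply is that the problem may never arise. It needs GCase results above ULOQ and no in-range result after dilution, and the documents show neither. Section 4 is a general rule qualified by the words as applicable, and the laboratory manual, which is not available here, may already require dilution. This stands. It makes the point conditional, although it also means that a reader of the final tables could not tell an assay ceiling from biology.

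The size also depends on the design as run. Protocol Section 13.3.1 plans at least two participants per cohort, allows a single one in defined circumstances, and allows planned cohorts to be left untested. With only Cohorts 1 to 3 dosed, the bias is slight except at the lowest limit examined. At a ULOQ equal to the predicted Cohort 4 median, the four-cohort bias (0.06) is half of one sampling SD. The cohort geometric mean is more sensitive, at 18% too low in that setting.

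There is some protection already: listings show which results exceeded the limit, and medians resist capping of a minority of values. The summary tables and the regression carry no such flag.

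Two stronger readings are tempting, and the documents support neither.

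- A reader might set the predicted activities against the protocol's example lower limit of normal (1.5 µmol/L/h) and conclude that the assay ceiling must be exceeded. A normal-range limit says nothing about a ULOQ. Its matrix is unstated, and the protocol says that it varies by laboratory.
- A reader might infer that a biased exponent would drive dose selection. No section makes SAP 10.4 an input to escalation or to the Part 2 dose. Those decisions use emerging safety, PK, PD and clinical data with DMC oversight, and SAP Section 14 states that the interim analysis will not be performed.

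Finally, replacing the planned regression outright would go too far. With about 12 participants, a censored fit leans on the assumed log-linear form when most of the top cohort is censored. A partly capped AUClast has a participant-specific bound that a single-limit censored model does not represent.

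**Conclusion.** The concern holds conditionally. The substitution rule is explicit, applies to PK parameters and is not overridden for GCase activity. Where it operates, Cmax and AUClast can only be understated. Where it operates mainly in the upper doses, the exponent is biased below its true value.

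The size cannot be fixed from the documents. Under the stated assumptions it runs from nil (mean slope about 1.00 at 8000 nmol/h/mL) to substantial (0.69 at about 1,290), and it is much smaller if Cohort 4 is not dosed. These figures rest on linear macaque-to-human scaling, log-SD 0.5, three participants per cohort and assumed plasma limits. Leukocyte and dried-blood-spot activity have no prediction to work from. The affected analyses are secondary or exploratory and descriptive; the primary safety endpoint is untouched. The point merits a correction to the SAP, but it does not show that the trial's results are or will be distorted.

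**What to change.** Amend the SAP for GCase activity as follows:

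- **Sections 4 and 10.1:** State the ULOQ for each matrix and the dilution and re-assay policy. Use the diluted re-assay result wherever the laboratory has one. Tabulate the number of results still above ULOQ by cohort and matrix.
- **Section 10.3:** Report any Cmax or AUClast that includes such a result as a lower bound (≥), not as an observed value.
- **Section 10.4:** If any such results occur, add a right-censored maximum-likelihood power model for ln(Cmax) as a sensitivity analysis beside the planned regression. Interpret AUClast with its lower-bound flag and do not force it into the same model.

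The cost is SAP wording, one extra table and, if needed, one standard model. Where values are censored, the interval for the exponent will be wider. If no result exceeds ULOQ, nothing in the results changes.
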